2.3 Additional Data

Demographics and baseline characteristics, procedure information, and adverse events. For additional information, refer to the PDA Module in **Appendix C.**

3 STUDY POPULATION

Participating subjects includes infants born prematurely (<37 weeks' gestation) with a weight less than 2 kg at the time of device implant. The decision to close the PDA is entirely at the discretion of the referring/primary cardiologist or neonatologist.

3.1 Inclusion Criteria

To participate in this clinical study, subjects must meet all of the following inclusion criteria:

- a. Diagnosis of a PDA
- b. Clinical indication for transcatheter PDA closure (discretion of the physician)
- c. Weight < 2 kg at the time of device implant

All participating study sites must obtain center specific IRB approval to enter patient data in the case reporting form (CRF) which will be called the PDA module. Individual consents from the subjects (or legally authorized representative) is not required unless local laws and governing IRB requirements require obtaining informed consent for data entry to this registry. No deviation of standard clinical practice is expected for participating in this study. No special pre-procedure, post-procedure, and follow-up testing is required for the purpose of this clinical study.

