1.2 Study Design

This is a multi-center, single arm, non-randomized, observational study designed to help assure continued safety and effectiveness of FDA approved Amplatzer Piccolo Occluder device for PDA closure in premature infants less than 2 kg at the time of device implant. The study will be conducted at all the CCISC participating sites.

Subjects will have transcatheter PDA closure using the Amplatzer Piccolo Occluder device as part of standard clinical practice under fluoroscopy with or without additional echocardiographic image guidance. The study involves collecting and reporting of data for the ASO II AS PDA closure procedures into the CCISC PDA Module Database. The PDA module encompasses pre-procedure, procedure, 48-hoours, 1-month and 6-months post-procedure follow-up data entry. It also encompasses an adverse event reporting system. Data entry is expected for all attempted PDA closure procedures in which the Amplatzer Piccolo Occluder device is attempted in premature infants weighing < 2 kg at the time of the procedure. It includes pre-procedural and postprocedural echocardiographic information as well as data from procedural echo guidance if utilized. Follow-up will be for a period of six months +/- 30 days after the procedure.

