4 STUDY PROCEDURES

The indication to choose transcatheter PDA closure is at the discretion of the referring and implanting physician. No deviation of standard clinical practice is expected to participate in this study. No special pre-procedure, post-procedure, and follow-up testing is required for the purpose of this clinical study.

Enrolled subjects (as defined in section 3.1) will undergo a PDA closure procedure with the appropriate device size deemed suitable for that particular patient. Post-procedure, the subject will need a follow-up within 48-hoours, 1-month and 6-months after the procedure. The Principal Investigator should arrange for appropriate care of subjects following study completion.

This will be a prospective data input Registry. Screen fail subjects who do not have a PDA closure attempt or those who have the Amplatzer Piccolo Occluder device introduced but do not retain an

Amplatzer Piccolo Occluder PDA closure device at the end of the procedure will be noted in the Registry and followed for 48 hours postprocedure.

The following sections provide a detailed description of procedures required by this clinical study.

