5.6 Risk-to-Benefit Rationale

Risks associated with participating in this clinical study are not anticipated to be any different from risks associated with participating in any other large web-based registry. There is a small risk of a loss of confidentiality and every effort will be made to prevent this type of breach. The potential benefit of participating in this clinical study will allow for a large data registry to be compiled. Advantage of having this registry will include the possibility of future prospective, observational and cohort studies. The PDA module, though initially for the Amplatzer Piccolo Occluder device, will also provide a method for tracking and oversight for all PDA device procedures in the United States.

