7.4 Analysis Population

The analysis of the primary and secondary endpoints will include all subjects who achieve a successful implant, which is defined as leaving the catheterization lab with a device implanted in the PDA. If a subject has multiple devices attempted during the same procedure, but leaves procedure with at least one device within the PDA the procedure is considered successful. Subjects without an implanted device in the PDA will be excluded. Additionally, subjects who had no follow- up visits up to the six-months +/- one-month window, or lost to follow-up will be excluded.

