7.6. Justification of Clinical Study Design

Based on the IMPACT registry, there are over 6000 transcatheter device closures of PDA that occurs in the United States annually. However, there are no comprehensive data collection tools for this procedure. The current databases do not include multiple data points, or follow-up data, or a section for specific adverse events to be documented. Moreover, until now, there has been no approved devices for PDA closure in children < 2kg. This clinical study is the first of its kind to collect data from all transcatheter device closure of PDA in children < 2kg performed at the CCISC participating centers. This study will be limited to children between 700 to 2000 grams who are the most vulnerable population undergoing this procedure. This will allow us to understand the real world experience (efficacy and safety) of using the Amplatzer Piccolo Occluder device in an extremely vulnerable, yet highly underserved population. The study will allow for standardization of this procedure throughout the country for the small children (<2 kg) with a PDA. This is a multicenter, single arm, observational data collection study. This will be a large population study to help analyze outcomes in subjects <2 kg. The trial has two primary endpoints for safety and effectiveness without formal hypothesis. The safety and effectiveness results will be compared with data reported in the Amplatzer Piccolo Occluder IDE and Continued Access Protocolstudies.

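### Section 1.2 limits the study to procedures in which the Piccolo is attempted, but the eligibility, enrolment and analysis sections do not carry that limit over, and 7.6 contradicts it

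*Protocol*

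**What the plan says.** **Text that limits the study to the Piccolo.** Section 1 gives the purpose as evidence on PDA closure with this device. Section 1.2 says subjects will have closure with it, and sets the data-entry scope: "Data entry is expected for all attempted PDA closure procedures in which the Amplatzer Piccolo Occluder device is attempted in premature infants".

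**Text that decides entry and analysis.**
- Section 3: "Participating subjects includes infants born prematurely (<37 weeks' gestation) with a weight less than 2 kg at the time of device implant". No device is named.
- Section 3.1: three criteria, namely a PDA, weight below 2 kg, and "Clinical indication for transcatheter PDA closure (discretion of the physician".
- Section 3.2: seven exclusions, none about the device.
- Section 4: "Enrolled subjects (as defined in section 3.1) will undergo a PDA closure procedure with the appropriate device size". Enrolment thus points back to 3.1.
- Section 7.2: the planning figure of about 99% occlusion is given for subjects implanted with any device.
- Section 7.4: "The analysis of the primary and secondary endpoints will include all subjects who achieve a successful implant". Success means leaving the catheterization lab with a device in the PDA, and the device is not specified.
- Section 7.5a: implant success is computed over all subjects entered in the PDA module.
- Section 7.6: the study will "collect data from all transcatheter device closure of PDA in children < 2kg performed at the CCISC participating centers".

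The primary rates are then compared with the Piccolo IDE and Continued Access studies (7.1 and 7.6; section 7.2 calls the first of these ADO II AS).

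**The concern.** A study of one device needs a rule that ties each counted subject to that device. Here the tie is in the design section only. The sections that a site uses to decide whom to enter, and that an analyst uses to build the denominators, leave it out, and 7.6 states a wider scope outright.

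Two things are at stake. First, infants in whom no Piccolo was ever used could shift both primary rates, in an unknown direction, away from what the Piccolo comparators measure. A larger sample would not remove that shift. Second, each such infant would take one of the 500 places in the initial cohort (section 2 and section 13) without adding information on the Piccolo.

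**Working it through.** The protocol gives no derivation of the 500 and tests no hypothesis (7.6), so there is no planned figure to reproduce. The check is mainly a reading of the sections against each other.

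**Step 1. Follow one infant through the rules.** Take a premature infant of 1.5 kg with a PDA and a clinical indication, closed from the start with another occluder and seen at six months.

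| Rule | Result |
|---|---|
| 1.2, device and data-entry scope | Outside: no Piccolo attempt |
| 3, 3.1, 3.2 | Meets the population statement and all three criteria; no exclusion applies |
| 4, enrolled | Enrolled, because the definition refers to 3.1 |
| 4, 48-hour-only group | Not in it: a closure was attempted, and no Piccolo was introduced and then not retained |
| 7.4 | Included: a device is in the PDA and there is follow-up |
| 7.5a | Included once entered in the module |
| 7.6 | Within the stated scope |

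Section 1.2 keeps the infant out. The other rules, read literally, let the infant in. No section says which prevails. Section 8.1 defines a deviation as failure to follow the protocol's requirements generally and gives failure to adhere to the inclusion/exclusion criteria as an example, but those criteria contain nothing on the device.

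**Step 2. Can the data separate the groups?** Appendix C lists each device used, with its outcome, and has a device type entry for each implanted device. A non-Piccolo implant can therefore be identified.

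**Step 3. Scale, under assumptions.** The documents give neither the share *f* of non-Piccolo infants nor device-specific rates. The only relevant figure is the overall literature range for major complications in 7.1, 4.0% to 10.0%. Assigning its two ends to the two groups is an assumption made only to bound the arithmetic:

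pooled rate = (1 − *f*) × Piccolo rate + *f* × other-device rate

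| Assumed *f* | Places of 500 | Piccolo 4%, other 10% | Piccolo 10%, other 4% |
|---|---|---|---|
| 2% | 10 | 0.98×4 + 0.02×10 = 4.12% | 0.98×10 + 0.02×4 = 9.88% |
| 5% | 25 | 0.95×4 + 0.05×10 = 4.3% | 0.95×10 + 0.05×4 = 9.7% |
| 10% | 50 | 0.90×4 + 0.10×10 = 4.6% | 0.90×10 + 0.10×4 = 9.4% |
| 20% | 100 | 0.80×4 + 0.20×10 = 5.2% | 0.80×10 + 0.20×4 = 8.8% |

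For comparison, the exact (Clopper-Pearson) 95% interval is 2.5% to 6.1% for 20 events in 500 (4%) and 7.5% to 13.0% for 50 in 500 (10%). Every pooled value in the table lies inside the matching interval. The exclusions in 7.4 would reduce the denominator below 500 and widen the intervals.

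**The case against.** The strongest reply is that the protocol must be read as a whole and that the Piccolo runs through it. Section 1 states the purpose, 1.2 states the device and the data-entry scope, 4.3 describes implanting only the Piccolo, 5.5.1 asks for operators with expertise in it, and section 4 lists special dispositions only for no closure attempt or a Piccolo not retained. On that reading, leaving the device out of 3.1 is drafting economy. This stands to a considerable degree. A reader of 3.1 and 7.4 might infer that the protocol plainly admits infants treated from the start with another occluder. It does not: 1.2 excludes them. What remains is a contradiction, since 7.6 states a wider scope and the enrolment and analysis definitions follow 3.1.

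Section 5.6 is also tempting as support, because it says the module "will also provide a method for tracking and oversight for all PDA device procedures in the United States". That sentence opens by saying the module is initially for the Piccolo, and its subject is the database platform, not this study's cohort. It shows only that other-device entries may come to share the database, which makes 7.5a's use of all module entries unsafe. Likewise, the device type field in Appendix C also serves multiple or replacement devices within a Piccolo procedure and does not show that other-device cases are admitted.

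Finally, 7.6 says no device was previously approved below 2 kg, which might suggest that other-device closures are rare. That does not rule out such use: 5.5.1 itself refers to earlier experience with similar devices in subjects below 2 kg. The documents support no particular share either way.

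**Conclusion.** The point holds as an internal contradiction about who enters the cohort and the primary rates. Section 1.2 restricts the study to attempted Piccolo procedures. Sections 3.1, 3.2, 4, 7.4 and 7.5a do not carry the restriction over, 7.2 speaks of any device, and 7.6 contradicts it.

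A reader might go further and infer that the primary rates are biased by a stated amount. The documents do not support that. The 2% to 20% shares and the 4% versus 10% split are assumptions, and even under them the shift is at most 1.2 percentage points and stays within sampling error at 500. The comparison with the earlier studies is made without a formal hypothesis, so no decision rule turns on it. The case for change is that the inconsistency concerns the denominator of both primary endpoints and is cheap to remove.

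An infant in whom a Piccolo was attempted and another device left in place is a different matter. That infant falls within 1.2 and meets the implant condition of 7.4, yet section 4 provides only 48 hours of follow-up. The revised 7.4 wording should not leave that case open.

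**What to change.** 1. **Section 3.1:** add a criterion that the procedure was begun with the Amplatzer Piccolo Occluder as the intended device. Tie it to 1.2's notion of an attempt and count it from the start of the procedure. Requiring that the device was introduced into the infant would be too narrow: it would drop infants injured at vascular access before introduction and so flatter the implant-success rate in 7.5a and the complication counts.
2. **Sections 7.4 and 7.5a:** restrict both cohorts to subjects meeting that criterion, using the device information in the CRF, and state in 7.4 which device counts as a successful implant.
3. **Sections 7.2 and 7.6:** replace the references to any device and to all transcatheter closures with wording that matches 1.2.
4. **Sections 2 and 13:** state that module entries without a Piccolo attempt do not count toward the 500.

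The cost is one inclusion line and a few wording changes. The device used is already recorded. The form as reproduced shows no entry for the intended device, so a procedure abandoned before any device was introduced may need one extra field. The downside is that non-Piccolo entries no longer count toward the 500, so accrual may take longer if there are many. No treatment or visit changes.

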3.2 Exclusion Criteria

Subjects who meet any of the following exclusion criteria must be excluded from the clinical investigation:

- a. Weight <700 gm or ≥ 2 kg at the time of device implant
- b. Age < 3 days at the time of device implant
- c. Pre-existing coarctation of the aorta
- d. Pre-existing left pulmonary artery stenosis
- e. Cardiac output that is dependent on right to left shunt through the PDA due to pulmonary hypertension
- f. Intracardiac thrombus that interferes with device implant
- g. Active infection requiring treatment at the time of implant

The indication to choose transcatheter PDA closure is at the discretion of the referring and the implanting physician. Though the above stated exclusion criteria are standard for most patients undergoing transcatheter PDA closures, clinical discretion is advised for each subject selection.

4 STUDY PROCEDURES

The indication to choose transcatheter PDA closure is at the discretion of the referring and implanting physician. No deviation of standard clinical practice is expected to participate in this study. No special pre-procedure, post-procedure, and follow-up testing is required for the purpose of this clinical study.

Enrolled subjects (as defined in section 3.1) will undergo a PDA closure procedure with the appropriate device size deemed suitable for that particular patient. Post-procedure, the subject will need a follow-up within 48-hoours, 1-month and 6-months after the procedure. The Principal Investigator should arrange for appropriate care of subjects following study completion.

This will be a prospective data input Registry. Screen fail subjects who do not have a PDA closure attempt or those who have the Amplatzer Piccolo Occluder device introduced but do not retain an

Amplatzer Piccolo Occluder PDA closure device at the end of the procedure will be noted in the Registry and followed for 48 hours postprocedure.

The following sections provide a detailed description of procedures required by this clinical study.

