7.1 Primary Safety Endpoint

The primary safety endpoint is the rate of major adverse events through up to six-months after an attempted device implant (refer to **Appendix A** for definition).

The proportion of subjects experiencing a major AE through up to six-months will be estimated. The 95% confidence interval for the percent of major AE will be calculated using the exact binomial method. The numerator for the event rate is the number of subjects who experienced an event through up to six-months. The denominator is the number of subjects in the analysis population (As detailed in Section 7.4). The primary safety endpoint rate will be descriptively compared with the rate reported in the Amplatzer Piccolo Occluder IDE and Continued Access Protocol studies. The overall estimated rate for major complications based on published literature ranges between 4.0 to 10.0%.

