7.5 Other Endpoints

The following endpoints will be summarized using descriptive statistics.

a. **Implant success:** The frequency and percentage of implant success (defined in Section 7.4) will be reported. This analysis will include all subjects entered in the PDA module.

- b. **PDA shunt status at follow-up visit**: The frequency and percentage of PDA shunt status at the 6 month follow-up visit, as assessed by the TEE, will be reported. Shunt sizes categories are: Grade 0/1, 2, and Grade 3/4. This analysis will include subjects who achieve a successful implant.
- c. **Obstruction measurements at follow-up visit**: The frequency and percentage of significant obstruction of the left pulmonary artery and the frequency and percentage of significant aortic obstruction (defined in Section 7.3) at the 6 month follow-up visit will be reported. Both analyses will include subjects who achieve a successful implant.
- d. **Major and Minor Complications**: The frequency and percentage of major and minor complications (refer to **Appendix A** for definition) from the time of the implant procedure will be reported.
- e. **Death**: The frequency and percentage of death will be reported.
- f. **Additional data**: Demographics and baseline characteristics, procedure information, left ventricular function and dimensions, pulmonic and tricuspid regurgitation, adverse events, subjects lost to follow-up will also be summarized.

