8.2 Safety reporting

Safety surveillance within this study (and the safety reporting performed by the investigator), starts as soon as the subject is referred for PDA closure. The safety surveillance and the safety reporting will continue until the follow-up visit has been performed, the subject is deceased, the subject/investigator concludes his/her participation into the clinical study or the subject is deemed lost to follow-up. All adverse event data required to be reported will be collected throughout the clinical study and will be reported to the CCISC PDA Module PI.

For the purposes of this clinical study the following events will be reported (see **Appendix A** for definitions):

- a. Unanticipated adverse device effects
- b. All adverse events viewed/interpreted by investigator to be potentially related to either i) the implant procedure or ii) the device regardless of seriousness

Note – If relatedness is unknown or cannot be determined, then the event must be reported.

Note – if a procedure is abandoned and surgical ligation is used to close the PDA, adverse events associated with the surgical ligation will not be reported.

Records relating to the subject's subsequent medical course must be maintained and submitted (as applicable) to the CCISC PDA Module PI until the event has subsided or, in case of permanent impairment, until the event stabilizes and the overall clinical outcome has been ascertained. Adverse events will be monitored until they are adequately resolved. The status of the subject's condition should be documented at periodic intervals.

Subject deaths will be documented and reported to the CCISC PDA Module PI as soon as possible (but no later than 3 business days) after becoming aware of the event via the applicable CRF. If an unanticipated adverse device effect occurs, the investigator must notify the CCISC PDA Module PI and the IRB immediately, but no later than 10 working days of the investigator's knowledge of the event, as required by 21 CFR §812.150. The CCISC will take any steps necessary to investigate the event, and, as appropriate, will be responsible for notifying FDA and all other participating IRBs and investigators.

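### Infants with an introduced but not retained Piccolo are followed for only 48 hours, which does not fit a safety endpoint anchored to the attempted implant and running to six months

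*Protocol*

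**What the plan says.** Section 4 (Study Procedures) sets the general schedule of contacts at 48 hours, 1 month and 6 months. It then makes a separate rule for two kinds of infant. The sentence opens with "Screen fail subjects who do not have a PDA closure attempt or those who have the Amplatzer Piccolo Occluder device introduced but do not" retain one, and says that subjects with no device "at the end of the procedure will be noted in the Registry and followed for 48 hours postprocedure".

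Other parts of the protocol bear on the same infants:

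- Section 1.2: "Data entry is expected for all attempted PDA closure procedures in which the Amplatzer Piccolo Occluder device is attempted". Later in that paragraph, as a general statement: "Follow-up will be for a period of six months +/- 30 days after the procedure".
- Section 7.1: the primary safety endpoint is the rate of major adverse events "through up to six-months after an attempted device implant".
- Appendix E: adverse event and death data are scheduled at implant, within 48 hours, at 30 days and at 6 months, with no separate line for infants without a device.
- Section 8.2: "The safety surveillance and the safety reporting will continue until the follow-up visit has been performed", or until death, end of participation or loss to follow-up. Events already reported are followed until they resolve or stabilise. Adverse events of a surgical ligation after an abandoned procedure are not reported.
- Section 7.4: infants without an implanted device are left out of the primary and secondary analyses.
- Section 7.5: items b and c are limited to successful implants. Item d (major and minor complications) and item e ("The frequency and percentage of death will be reported") name no population.

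**The concern.** An infant never attempted has had no exposure to the procedure. An infant in whom the device was introduced and removed has had vascular access, catheter manipulation and usually anaesthesia or sedation. Section 4 gives both the same two days of observation.

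The safety outcomes do not all appear within two days. Section 2.1 counts access complications first seen more than 24 hours after the procedure, with loss of a limb at the severe end. Appendix A counts procedure-related death, lasting disability and femoral vessel thrombophlebitis treated with intravenous antibiotics as major complications. None of these needs a device left in the duct. A site that follows Section 4 has no scheduled contact at which to learn of them after 48 hours. A site that follows Appendix E has two.

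At stake is whether a complication or death percentage that includes failed attempts can be read as a six-month figure. If these infants stand in the denominator but can scarcely contribute events after day 2, the percentage can only be too low. Adding them to a safety denominator without changing Section 4 would not help, because the late data would not exist.

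**Working it through.** The protocol gives no figure on this point to reproduce. There is no hypothesis test or sample-size calculation, and no non-retention rate is stated. Two checks are possible.

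**1. Share of the window not observed.** Inputs: 48 hours, i.e. 2 days (Section 4); six months plus or minus 30 days (Section 1.2), taken as 180 days with a range of 150 to 210. Unobserved share = 1 − 2/T.

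- T = 150: 1 − 2/150 = 98.7%
- T = 180: 1 − 2/180 = 98.9%
- T = 210: 1 − 2/210 = 99.0%

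This rests only on the protocol's own time points.

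**2. Events that might be missed.** Inputs: 500 subjects (Sections 2 and 13), here taken to include failed attempts; a non-retained fraction f, assumed 1% to 10%; a rate q of new complications or death after 48 hours among these infants, assumed 5% to 20%. Neither f nor q is in the protocol. Missed events = 500 × f × q.

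| f | infants | q | missed events | points of 500 |
|---|---|---|---|---|
| 1% | 5 | 5% | 0.25 | 0.05 |
| 5% | 25 | 10% | 2.5 | 0.5 |
| 10% | 50 | 20% | 10 | 2.0 |

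As a cross-check, replace q with the 4% to 10% that Section 7.1 gives from the literature for major complications, and suppose that all of them arose after 48 hours. The range becomes 5 × 4% = 0.2 to 50 × 10% = 5 events, or 0.04 to 1.0 points.

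For scale, 4% and 10% of 500 are 20 and 50 subjects, with exact 95% intervals of 2.5% to 6.1% and 7.5% to 13.0%. The possible shift lies within ordinary sampling error at most of the assumed values. Unlike sampling error, it always goes in one direction.

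**Which analyses are touched.** Section 7.4 removes these infants from the primary and secondary endpoints, so those estimates do not change with the 48-hour rule. Items 7.5d and 7.5e carry no limit to successful implants, whereas 7.5b and 7.5c do. If attempted infants are counted in d and e, their follow-up is about 2 days against about 180 for the rest. The same applies to any rate reported per attempted implant, which is how Section 7.1 words its endpoint.

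**The case against.** The strongest reply is that Section 4 states a specific exception to a general schedule, and that the specific text governs. Section 1.2 does not tie the six months to attempted procedures: its data-entry sentence and its follow-up sentence are separate. Section 8.2 can be squared with Section 4 if the 48-hour contact is these infants' last visit. The ligation note in 8.2 shows that limiting collection after a failed attempt was in part deliberate. With no device retained, delayed embolization and stenosis caused by an implant largely drop out, which leaves mainly delayed access complications and death. Events reported by 48 hours are followed to resolution. The population for 7.5d and 7.5e may be set in an SAP that is not at hand.

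Much of this stands, and it rules out several stronger readings that a reader might infer:

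- That Section 1.2 in terms requires six months for every attempt. It does not; the link is made by reading the paragraph together.
- That the protocol labels these infants screen failures. The sentence can equally be read as naming two groups. Both get 48 hours either way.
- That every late consequence is lost. A thrombosis reported on day 1 that worsens later is still followed under 8.2; only events with onset after 48 hours are at risk.
- That the primary safety estimate is biased by this rule. Section 7.4 excludes these infants from it.

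What the reply does not answer is Section 7.1, which starts the safety clock at the attempt and runs it to six months, and Appendix E, which makes no exception. The ligation note in 8.2 excludes only ligation events, so other events after an abandoned procedure appear to remain reportable. The adverse event form in Appendix D also provides for retrieval without another device. No reason is given for stopping at 48 hours.

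**Conclusion.** The point holds in a limited form. Section 4 does not fit Section 7.1 or Appendix E, and sits uneasily with the general follow-up in Section 1.2. Followed as written, it leaves new procedure-related events and deaths after 48 hours without systematic collection for infants whose attempt failed. Some may still reach the registry if an investigator reports them unprompted.

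The loss of about 99% of the observation window is firm. The event count is not: under 1 to about 10 per 500, on assumed non-retention of 1% to 10% and assumed late rates of 5% to 20%. The effect reaches the Section 7.5 complication and death summaries only if attempted infants are counted there, which is inferred from the absence of a stated restriction. The study is descriptive and its primary and secondary estimates are untouched, so this is a worthwhile, inexpensive correction and not a threat to the main results.

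**What to change.** In Section 4, separate the two groups. Keep the 48-hour limit for infants with no closure attempt. For any infant in whom the Piccolo was introduced, whether or not it was retained, collect device- or procedure-related adverse events and death to six months from routine-care records, with no added test or visit. Keep the exclusion of surgical-ligation events in Section 8.2.

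Then reconcile Sections 1.2, 4, 7.1, 8.2 and Appendix E so that they give one follow-up period for attempted procedures, and state the population for items 7.5d and 7.5e.

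The cost is protocol wording plus adverse event and death entry for an assumed 5 to 50 infants in 500. The downside is slightly more data entry at sites, and some effort to trace infants who have moved to another hospital.
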